### **6.13.3. Deaths, Other Serious Adverse Events, and Other Notable Adverse Events**

An overview of AEs, including the number and percentage of patients who died or suffered SAEs during the study, discontinued due to AEs and who suffered TEAEs, will be provided. Comparison between treatments will be performed using Fisher's Exact Test.

### **6.13.4. Clinical Laboratory Evaluation**

Laboratory measurements will be analyzed using continuous data (change from baseline) and categorical or ordinal data (proportion of treatment-emergent abnormalities). If there are multiple records of laboratory measurements at baseline or postbaseline visit, the last record will be used. Summaries and analyses of continuous data (change from baseline) will be performed using both conventional and International System of Units (SI units).

Measures of central tendency for planned lab analytes' raw measurements and change from baseline (in CN and SI units) will be summarized with boxplots. Boxplots will display results semi-annually (visits 8, 15, 22, and 28) and for the last visit (LOCF) and will include summary tables of N, mean, median, quartiles, min, max, standard deviation, and p-value (for change scores). If there are considerable missing visits, the measures of central tendency may be based on MMRM analyses.

Treatment differences in the proportion of patients with treatment-emergent high or treatment-emergent low or treatment-emergent abnormal laboratory values at (1) anytime and (2) semi-annually (visits 8, 15, 22, and 28) will be assessed using Fisher's exact test. Treatment-emergent high or low laboratory abnormality will be based on SI unit. For each laboratory analyte, only patients who were low or normal at all baseline assessments and have at least 1 post-baseline will be included in the denominator when computing the proportion of patient with treatment-emergent high. Similarly, only patients who were high or normal at all baseline assessments and have at least 1 post baseline will be included in the denominator when computing the proportion of patient with treatment-emergent low. In addition, treatment differences in the proportion of patients who have normal baselines with a change to abnormal high or abnormal low values at any post-baseline visits will be summarized.

For urinalysis parameters, baseline to post-baseline shifts will be summarized at each protocol-specified visit. Likelihood ratio chi-square tests will be used to compare increase, no change, and decrease shifts in urinalysis parameters between treatment groups at each visit.

The proportion of patients with treatment-emergent clinically significant changes from a low value or normal value at all baselines at any time in ALT and total bilirubin will be summarized by treatment group. Clinically significant changes of interest at any time are: ALT  $\geq 3$  x upper limit of normal (ULN) and total bilirubin  $\geq 2$  x ULN, AST  $\geq 3$  x ULN, ALT  $\geq 5$  x ULN, ALT  $\geq 10$  x ULN, and total bilirubin  $\geq 2$  x ULN. Additionally, Hy's Law analysis will be conducted by comparing treatment groups with regard to the proportion of patients with (ALT  $\geq 3$  x ULN OR AST  $\geq 3$  x ULN) AND total bilirubin  $\geq 2$  x ULN at any time. Comparisons between treatment groups will be carried out using Fisher's Exact test. When criteria are met for hepatic evaluation

and completion of the hepatic safety case report form (CRF), investigators are required to answer a list of questions pertaining to the patient's history, relevant pre-existing medical conditions, and other possible causes of liver injury. A listing of the information collected on the hepatic-safety CRF will be generated.

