### **6.13.6. Electrocardiograms**

ECG measurements will be analyzed using continuous data (change from baseline) and categorical data (proportion of treatment-emergent abnormalities) using the Safety Dataset.

The ECG measurements are derived from three 10 second readings taken every 30 seconds. These 3 readings are to be averaged prior to analysis. Additionally, whenever ECG is measured in triplicate, the average of these readings will be used in the analysis. If there are multiple records after averaging ECG triplicates within a visit, the last record of averages will be used.

The analysis will be done for the following ECG measurements: heart rate, PR, QT, QTc, and RR intervals and QRS duration. All analyses of QTc will be carried out using the Fridericia correction (QTcF) method. Measures of central tendency for ECG raw measurements and change from baseline will be summarized with boxplots. Boxplots will display results semi-annually (visits 8, 15, 22, and 28) and for the last visit (LOCF) and will include summary tables of N, mean, median, quartiles, min, max, standard deviation, and p-value (for change scores). If there are considerable missing visits, the measures of central tendency may be based on MMRM analyses.

In order to assess outliers and potentially clinically significant changes from baseline, the number and percent of patients meeting criteria for treatment-emergent abnormalities in ECGs will be summarized. Treatment group comparisons will be performed using Fisher's exact test. Baseline is defined as the entire screening period (visits 1 and 2), and all baseline assessments must not meet abnormality criteria to be included in the analysis. Incidence of treatment-emergent abnormal ECGs will be assessed by comparisons at (1) anytime and (2) semi-annually (visits 8, 15, 22, and 28).

Abnormal ECG criteria and criteria for abnormal QTcF prolongation are presented in [Appendix 2](#).

Treatment-emergent high ECG parameters (heart rate, PR interval, QRS duration, QT and QTcF intervals) are the values which are low or normal at all baseline visits and fall into the high abnormal categories post-baseline. Similarly, treatment-emergent low ECG parameters (heart rate, PR interval, QRS duration) are the values which are high or normal at all baseline visits and fall into the low abnormal categories above.

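### The marked ALT and bilirubin counts, and most naturally the QTcF >500 msec count, leave out patients who were above normal at any baseline visit, so some extreme values enter no comparison by arm

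*SAP*

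**What the plan says.** **Liver tests (SAP 6.13.4).** For any treatment-emergent high laboratory value, "only patients who were low or normal at all baseline assessments and have at least 1 post-baseline will be included in the denominator". The paragraph on marked liver changes repeats the restriction: it summarises "treatment-emergent clinically significant changes from a low value or normal value at all baselines at any time in ALT and total bilirubin". The sentence beginning "Clinically significant changes of interest at any time are" then names ALT ≥3x ULN with total bilirubin ≥2x ULN, AST ≥3x ULN, ALT ≥5x ULN, ALT ≥10x ULN, and total bilirubin ≥2x ULN. Next comes a separate comparison: "Hy's Law analysis will be conducted by comparing treatment groups with regard to the proportion of patients with" ALT or AST ≥3x ULN together with total bilirubin ≥2x ULN. No baseline condition is attached to it. The section ends with a listing: "A listing of the information collected on the hepatic-safety CRF will be generated".

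**ECG (SAP 6.13.6 and Appendix 2).** The rule for entering the analysis of outliers is that "all baseline assessments must not meet abnormality criteria to be included in the analysis". The baseline window for this rule is screening, that is, Visits 1 and 2 together. Treatment-emergent high ECG parameters, QTcF among them, "are the values which are low or normal at all baseline visits and fall into the high abnormal categories post-baseline". Appendix 2 gives the high criteria for QTcF as ≥450 msec for males, ≥470 msec for females and >500 msec for both sexes. A separate table gives QTcF increases of >30, >60 and >75 msec and states no denominator.

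**The concern.** A normal-baseline rule suits a shift across a single limit, because a patient already above that limit cannot newly cross it. It does not suit thresholds far above the limit. Going from just over ULN to 10x ULN, or from just over 450 msec to above 500 msec, is a new and large change whatever the starting category. The rule is also strict: one high value at any baseline assessment removes the patient, even if the last value before dosing is normal, whereas the general definition in 6.1 takes only the last pre-dose measurement as baseline.

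The patients removed start closest to the thresholds. Events of this kind are usually few, so a comparison of counts by arm can depend on one or two patients.

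**Working it through.** The plan states no figure to reproduce. The check applies the written rules to example patients and then looks for any other planned count that would catch them.

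**Inputs.** Liver thresholds and baseline rule: 6.13.4. ECG baseline rule: 6.13.6. QTcF limits: Appendix 2. Trial size, for illustration only: 360 (5.2) or about 225 (title page). The SAP gives both.

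**Example patients (hypothetical values)**

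| Patient | Baseline | Later value | Result under the written rules |
|---|---|---|---|
| A | ALT 1.1x ULN at one baseline assessment | ALT 11x ULN; bilirubin and AST normal | Not in ALT ≥5x or ≥10x; not in Hy's Law (bilirubin normal) |
| B | As A, bilirubin normal | ALT 11x ULN, bilirubin ≥2x ULN | In Hy's Law and in bilirubin ≥2x; still not in ALT ≥5x or ≥10x |
| C | Man, QTcF 452 msec at one baseline visit | 505 msec | Not counted as >500 msec on the natural reading (452 ≥ 450) |
| D | Woman, QTcF 465 msec | 505 msec | Counted (465 < 470) |

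C rises by 505 − 452 = 53 msec and is left out. D rises by 505 − 465 = 40 msec and is counted. C's increase would meet the >30 msec criterion only, and only if that table is free of the baseline rule, which the SAP does not say.

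**Is there another count by arm?**
- The further summaries at the end of the general laboratory text in 6.13.4 and at the end of 6.13.6 are also limited to patients with normal baselines.
- Hy's Law catches joint transaminase and bilirubin rises only.
- Boxplots at visits 8, 15, 22, 28 and last visit may show a maximum, but not a number of patients, and they miss peaks between those visits.
- The listings in 6.13.4 and 6.16 show cases, not proportions.

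No count by arm of ALT ≥5x ULN, ALT ≥10x ULN, bilirubin ≥2x ULN alone or QTcF >500 msec regardless of baseline is planned.

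**Illustration of size.** Patients outside a count = N × share with a high baseline. The share is assumed; the SAP gives none.
- N = 360: 0.05 × 360 = 18; 0.15 × 360 = 54.
- N = 225: 0.05 × 225 = 11.25, about 11; 0.15 × 225 = 33.75, about 34.

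**The case against.** The best defence is that these tables are labelled treatment-emergent, define the term and apply it alike to every randomized arm. Nothing is misstated, and the proportions are valid for patients with normal baselines. That stands: the cost is lost sensitivity, with no built-in bias between arms.

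Some stronger readings are tempting but not supported:

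- **That the DMC would not see such patients.** It receives laboratory and ECG listings at the first interim (6.16.1), carried to the second (6.16.2), and a listing of abnormal laboratory values at the third (6.16.3). None is stated to be limited to treatment-emergent values. The third review names no ECG listing, and a listing gives no comparison by arm. Reported adverse events that worsen are also counted as treatment-emergent under 6.13.2, but that depends on reporting.
- **That a stand-alone ALT ≥3x ULN count is restricted.** The text reads most naturally as a joint criterion with bilirubin, and the unrestricted Hy's Law comparison covers it.
- **That AST is certainly restricted.** The restricting sentence names only ALT and total bilirubin. AST ≥3x ULN appears in the list that follows, so the restriction is probable rather than explicit.
- **That the QTcF >500 msec exclusion is certain.** The inclusion sentence could be applied row by row, in which case a man at 452 msec does not meet >500 msec at baseline and is counted later. The definition that follows points the other way but does not say whether normal is judged per row.
- **That the QTcF increase criteria are restricted.** No text says so; their denominator is simply not stated.

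**Conclusion.** The point holds for ALT ≥5x ULN, ALT ≥10x ULN and total bilirubin ≥2x ULN, and probably for AST ≥3x ULN. A patient above normal for that analyte at any one baseline assessment is in no planned by-arm count of its marked values, unless the Hy's Law criterion is also met. For QTcF >500 msec the same effect is the most natural reading for a man at ≥450 msec or a woman at ≥470 msec at baseline, but the wording leaves room for the other reading.

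The size is unknown. The 18 to 54 of 360 (or 11 to 34 of 225) rests on an assumed 5% to 15% share, used for liver tests and QTcF alike. A reader might take these figures as missed events. They are patients outside a denominator, and how many would reach an extreme value cannot be derived. Eligibility limits in the protocol, which is not at hand, could bring the share close to zero. The point concerns the sensitivity of the safety tables and does not touch the efficacy conclusions.

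**What to change.** In 6.13.4 and 6.13.6, add by-arm counts for ALT ≥5x and ≥10x ULN, AST ≥3x ULN, total bilirubin ≥2x ULN and QTcF >500 msec in all Safety patients with a post-baseline value. Split each row by baseline normal versus above normal. Keep the normal-baseline rule for the ordinary high/low shift tables. In Appendix 2, state that the QTcF increase criteria (>30, >60, >75 msec) use all patients with a baseline and a post-baseline value.

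The cost is SAP wording and some extra table rows; no new data are needed. The small downside is that some counted values will reflect elevation present before treatment, which the split by baseline status makes visible.

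### The liver threshold list in SAP 6.13.4 has no stand-alone ALT ≥3× ULN entry, so an isolated ALT rise of 3 to <5× ULN falls in no threshold category, while AST ≥3× ULN does

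*SAP*

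**What the plan says.** The hepatic part of SAP 6.13.4 has three components.

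- **Lead-in.** Treatment-emergent clinically significant changes, from a low or normal value at all baselines, "at any time in ALT and total bilirubin will be summarized by treatment group". AST is not named.
- **List of changes of interest.** It opens with "Clinically significant changes of interest at any time are: ALT $\geq 3$ x upper limit of normal (ULN) and total bilirubin" ≥2× ULN. The list continues with "AST $\geq 3$ x ULN, ALT $\geq 5$ x ULN, ALT" ≥10× ULN and closes with total bilirubin ≥2× ULN as a separate entry.
- **Hy's Law.** A further analysis follows: "Additionally, Hy's Law analysis will be conducted by comparing treatment groups" on the proportion with ("ALT $\geq 3$ x ULN OR AST $\geq 3$ x ULN) AND total bilirubin $\geq 2$ x ULN at any time".

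Earlier in 6.13.4, for laboratory analytes generally, the SAP compares by Fisher's exact test the "proportion of patients with treatment-emergent high or treatment-emergent low or treatment-emergent abnormal laboratory values at (1) anytime" and semi-annually. That comparison uses one high category per analyte, with no multiples of ULN.

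**The concern.** A graded liver summary lets the reader compare arms at rising multiples of ULN. Here the ALT scale starts at 5× unless bilirubin is also raised, while the AST scale starts at 3×. The SAP gives no reason for treating the two enzymes differently. The lead-in makes it odder, since it names ALT and not AST.

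An isolated ALT rise of 3 to <5× ULN is the mildest step on the plan's own 3× scale. If one arm had an excess of such rises, the listed thresholds would not show it. The general high-ALT count would include these patients, but mixed with every smaller rise above normal.

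The sentence is also hard to program as written. If the first entry is a combination, there is no ALT ≥3× row. If it is two criteria run together, bilirubin ≥2× is listed twice.

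**Working it through.** The SAP gives no figure to reproduce here, so the check applies its rules to patient profiles.

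**Rules (SAP 6.13.4), in multiples of ULN**

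- L1: ALT ≥3 and bilirubin ≥2
- L2: AST ≥3
- L3: ALT ≥5
- L4: ALT ≥10
- L5: bilirubin ≥2
- Hy: (ALT ≥3 or AST ≥3) and bilirubin ≥2
- TE-high ALT: ALT above normal after a low or normal baseline

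**Grid.** ALT at 0.8, 2, 4, 6, 12; AST at 0.8, 4; bilirubin at 0.8, 2.5. That is 5 × 2 × 2 = 20 profiles, of which 3 × 2 × 2 = 12 have ALT ≥3×. The profiles that decide the point, with TE-high read for a patient whose baseline ALT is low or normal:

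| ALT | AST | Bilirubin | Listed entries met | Hy's Law | TE-high ALT |
|---|---|---|---|---|---|
| 4 | 0.8 | 0.8 | none | no | yes |
| 0.8 | 4 | 0.8 | L2 | no | no |
| 4 | 4 | 0.8 | L2 | no | yes |
| 6 | 0.8 | 0.8 | L3 | no | yes |
| 4 | 0.8 | 2.5 | L1, L5 | yes | yes |
| 0.8 | 4 | 2.5 | L2, L5 | yes | no |

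**Gap.** Of the 12 profiles with ALT ≥3×, exactly one meets no listed entry: ALT 4, AST 0.8, bilirubin 0.8. Its mirror image, AST 4 with ALT 0.8, is counted under L2. In general the gap is ALT of 3 to <5×, AST <3× and bilirubin <2×.

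**Nesting.** L1 requires ALT ≥3 and bilirubin ≥2. Anyone meeting that also meets Hy, because ALT ≥3 satisfies the either-enzyme condition. The reverse fails only when AST alone is raised (last row), and that patient is still counted under Hy, L2 and L5. So L1 is a subset of Hy, and no combined case drops out.

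**With a stand-alone ALT ≥3× entry.** The first row of the table is then counted. The Hy's Law counts do not change.

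**Illustration only; all event rates are assumed.** SAP 5.2 gives 360 patients and the allocation is 1:1:1, so 360/3 = 120 per arm. When all k events fall in one of two arms of size n, the two-sided Fisher p-value is 2 × C(n,k)/C(2n,k).

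- 6 v 0 at ALT ≥3×: 2 × C(120,6)/C(240,6) = 0.029.
- If half stay below 5×, the ALT ≥5× entry shows 3 v 0: 2 × C(120,3)/C(240,3) = 0.247.
- The SAP title page instead gives about 225 patients, or 225/3 = 75 per arm. The same formula then gives 0.028 and 0.245.
- With 8 v 1 at ≥3× and 4 v 1 at ≥5×, 120 per arm, the two-sided Fisher values are 0.036 and 0.370.

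**The case against.** **These patients are not lost.** A reader might infer that ALT of 3 to <5× ULN is never counted. The SAP does not support that. From a low or normal baseline, such a patient is in the general treatment-emergent high ALT comparison. With bilirubin ≥2× the patient is in both the listed combination and Hy's Law, and with AST ≥3× in the AST entry. Change-from-baseline boxplots with quartiles and maximum also cover ALT. Individual values can be seen in the laboratory listings for the first and second interim analyses and in the abnormal-laboratory listing for the third (SAP 6.16). All of this stands and limits the point to isolated rises. It does not supply a comparison at 3×: the general count is ungraded, boxplots do not count patients over a threshold, and listings compare nothing. SAP 6.13.4 also provides a listing from the hepatic-safety case report form, but the SAP does not state what triggers that form, so whether it covers this group cannot be judged.

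**There is no contradiction with Hy's Law.** A reader might infer that the plan defines one signal in two incompatible ways. It does not. The list entry is not called Hy's Law, the Hy's Law analysis is introduced as an addition with its own criterion, and the first is nested in the second. A narrower and a broader criterion will give different counts without conflicting. What remains is redundancy that should be labelled or removed.

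**The p-values show little.** This stands as well. The rates are invented and placed either side of 0.05. They assume that none of the patients below 5× has AST ≥3×, they leave out the general high-ALT test, and the SAP attaches no decision rule to these comparisons. They show only how a count can shrink when the 3× step is missing.

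**Conclusion.** The point holds in a narrow form. Read literally, SAP 6.13.4 has a stand-alone entry for AST ≥3× ULN and none for ALT ≥3× ULN. An isolated ALT rise of 3 to <5× ULN (AST <3×, bilirubin <2×) therefore meets no graded liver threshold, and arms are compared on it only inside the ungraded high-ALT count. The plan's own use of 3× for ALT elsewhere in the paragraph makes this hard to read as deliberate.

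This rests on reading the first entry as a combination, which is the natural reading because bilirubin ≥2× recurs alone. The first mention of bilirubin may be a drafting slip for a stand-alone ALT ≥3× entry, but that is an inference.

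The consequence is confined to safety tabulation. The primary analysis, sample size and data collection are untouched. The number of patients affected cannot be derived from the SAP. The correction is still worth making, because following the list as written omits a comparison at a level the plan treats as meaningful, and adding it costs almost nothing.

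**What to change.** In SAP 6.13.4:

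1. Make ALT ≥3× ULN an entry of its own, so that the list reads ALT ≥3×, AST ≥3×, ALT ≥5×, ALT ≥10× and total bilirubin ≥2× ULN.
2. Name AST in the lead-in sentence beside ALT and total bilirubin.
3. Leave the enzyme-plus-bilirubin combination to the Hy's Law analysis. If the ALT-only combination is wanted as well, keep it as a labelled subset of Hy's Law so that the two counts are not mistaken for rival definitions.

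The cost is a wording change and one table row. No new data are needed, and the Hy's Law counts stay the same.

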### **6.13.5. Vital Signs and Other Physical Findings**

Vital sign measurements and weight will be analyzed using continuous data (change from baseline) and categorical data (proportion of potentially clinically significant changes) using the Safety Dataset.

If there are multiple records of vital sign or weight measurements at baseline or postbaseline visit, the last record will be used. Summary statistics will be presented for observed values at baseline and for change from baseline results at each scheduled postbaseline visit. Systolic and diastolic blood pressure and pulse (collected in sitting position), orthostatic diastolic and orthostatic systolic blood pressures and orthostatic pulse, temperature, and weight by treatment group for all patients in the safety population will be summarized.

Measures of central tendency for vital sign or weight raw measurements and change from baseline will be summarized with boxplots. Boxplots will display results semi-annually (visits 8, 15, 22 and 28) and for the last visit (LOCF) and will include summary tables of N, mean, median, quartiles, min, max, standard deviation, and p-value (for change scores). If there are considerable missing visits, the measures of central tendency may be based on MMRM analyses.

In order to assess outliers and potentially clinically significant changes from baseline, the number and percent of patients meeting criteria for treatment-emergent abnormalities in vital signs and weight at any time during study will be summarized. Treatment group comparisons will be performed using Fisher's exact test. Baseline is defined as the entire screening period (visits 1 and 2), and all baseline assessments must not meet abnormality criteria to be included in the analysis. Abnormal criteria for post-baseline vital signs and weight are presented in [Appendix 1](#). Any vital sign or weight meeting the criteria will be considered abnormal. Treatment differences in the proportion of patients with treatment-emergent abnormal high or low vital signs and weight will be assessed between treatment groups using Fisher's exact test at (1) any time (2) semi-annually (visits 8, 15, 22, and 28).

A listing of treatment-emergent abnormal vital signs and weight will also be presented.

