## 5. Study Design

### 5.1. Summary of Study Design

Study LMDC is a multicenter, randomized, double-blind, placebo-controlled, Phase 2 study of LY3303560 in patients with early symptomatic AD and low-to-medium cerebral tau burden. A combination of visual and quantitative assessments of tau PET is used to identify eligible patients:

- Visual assessment of AD+ (increased activity in posterior temporal regions only) AND  $1.10 < \text{SUVR} \leq 1.46$
- Visual assessment of AD++ (increased activity in temporal and parietal regions) AND  $\text{SUVR} \leq 1.46$

The maximum possible duration of the study is 121 weeks that includes a screening period of up to 8 weeks, a treatment period of 100 weeks, a 4-week post last dose assessment, and an immunogenicity and safety follow-up period of up to 13 weeks, following the last dose of the study drug at Week 100. Subjects who meet entry criteria will be randomized in a 1:1:1 ratio to one of the following treatments:

- **1400 mg LY3303560:** LY3303560 1400 mg IV infusion Q4W for 100 weeks (Visit 2 [Week 0] to Visit 27 [Week 100]).
- **5600 mg LY3303560:** LY3303560 5600 mg IV infusion Q4W for 100 weeks (Visit 2 [Week 0] to Visit 27 [Week 100]).
- **Placebo:** IV placebo infusion Q4W for 100 weeks (Visit 2 [Week 0] to Visit 27 [Week 100]).

The first safety review by a Data Monitoring Committee will be conducted after approximately 30 patients have received 3 doses and completed the 4 week assessment period ( i.e. just prior to their 4th dose). Enrolment will halt after these patients have received one dose of study treatment, however those patients already dosed will continue their allocated treatment. If any of these patients discontinue from study treatment for reasons other than safety, they may be replaced, upon discussion between the investigators and Lilly.

The primary hypothesis being tested is that LY3303560 administered for 100 weeks will result in a significant slowing in cognitive/functional decline compared with placebo as measured by the change from baseline to the end of the double-blind period (Week 104) on the integrated Alzheimer's Disease Rating Scale (iADRS), in subjects with early symptomatic AD (where early symptomatic AD refers to the combination of 2 stages: prodromal AD [mild cognitive impairment (MCI)-AD] and mild dementia due to AD; Alaka et al. 2015) who have low-to-medium tau burden.

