## 6. A Priori Statistical Methods

### 6.1. General Considerations

The protocol calls for a Data Monitoring Committee (DMC) charged with making decisions regarding patient safety and interim efficacy. This analysis plan describes analyses for the final clinical study report and all interim safety analyses for the DMC.

All analyses will follow the intention-to-treat (ITT) principle unless otherwise specified. An ITT analysis is an analysis of data by the groups to which subjects are assigned by random allocation, even if the subject does not take the assigned treatment, does not receive the correct treatment, or otherwise does not follow the protocol. Consistent with ITT studies the estimand for Study LMDC is the Treatment Policy estimand. Safety analyses will group subjects based on the actual treatment received. If a patient receives a treatment different than the randomized treatment for the duration of the placebo-controlled period, then that different treatment is the actual treatment; otherwise, the actual treatment is the planned treatment.

Unless otherwise noted, all pairwise tests of treatment effects will be conducted at a 2-sided alpha level of 0.05; 2-sided confidence intervals (CIs) will be displayed with a 95% confidence level. All tests of interactions between treatment and other factors will be conducted at an alpha level of 0.05.

Unless otherwise noted no formal statistical hypothesis testing will be made during the first safety interim. Any reported p-values that may be reported as part of standardized output are merely for information purposes only.

Unless otherwise noted baseline is defined as the last measurement prior to dosing. When change from baseline is assessed, subjects will only contribute to the analysis if both a baseline and a post-baseline measurement are available. Endpoint is the last non-missing post-baseline measurement within the time period for the given analysis. For mixed-effect model for repeated measures (MMRM) models, observations collected at nonscheduled visits will not be included in the analyses (Andersen and Millen 2013). For analyses using last observation carried forward (LOCF), the last nonmissing post-baseline observation (scheduled or unscheduled) will be used to calculate change from baseline.

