**Table 6.6.1. Analysis Populations for Study I8G-MC-LMDC**

Population	Description
Entered	All participants who sign informed consent
Randomized	All entered patients who are randomized to study treatment
Evaluable Efficacy	All randomized patients with at least one post-baseline iADRS13 result (protocol refers to this as the Full Analysis Set)
Safety	All randomized participants who take at least 1 dose of double-blind study treatment. Participants will be analyzed according to the actual treatment group received (actual treatment group is defined as the treatment received at Visit 2).
Per-Protocol	All subjects in the Evaluable Efficacy population who also: 
 
signed the inform consent form
 
had an assessment of the primary endpoint at each scheduled visit completed
 
had no violations of inclusion/exclusion criteria
 
had no study dosing algorithm violation (such as if subjects randomized to treatment A were given treatment B or subjects randomized to treatment A never received the assigned study drug)
 
had no unqualified raters and no raters with substantial scoring errors for the primary measure
 
were not considered non-compliant with regard to study drug (a subject is considered non-compliant when missing or incomplete infusions exceed 20%, OR if missed more than 3 consecutive infusions at any point)
 

Completers	All randomized subjects who have treatment disposition status of complete.
------------	--

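### Baseline for the vital-sign, weight and ECG abnormality tables is set by visit number and includes the first-infusion visit, with no restriction to pre-dose readings

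*SAP*

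**What the plan says.** SAP Section 6.13.5 sets the baseline for the categorical vital-sign and weight abnormalities: "Baseline is defined as the entire screening period (visits 1 and 2), and all baseline assessments must not meet abnormality criteria". Section 6.13.6 repeats the sentence for ECGs. Both sections also have a rule for several records at one visit. For vital signs and weight it is "If there are multiple records of vital sign or weight measurements at baseline or postbaseline visit, the last record will be used"; for ECGs it is "If there are multiple records after averaging ECG triplicates within a visit, the last record of averages will be used". Neither rule mentions dosing time.

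Three other places bear on this:

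- Section 6.1 gives the default: "baseline is defined as the last measurement prior to dosing". It applies only where nothing else is noted.
- Section 5.1 gives the low-dose regimen as "LY3303560 1400 mg IV infusion Q4W for 100 weeks (Visit 2 [Week 0] to Visit 27 [Week 100", and the other two arms run over the same visits. It counts screening and treatment as separate periods: the study "includes a screening period of up to 8 weeks, a treatment period of 100 weeks".
- Table 6.6.1, on the Safety population, says that the "actual treatment group is defined as the treatment received at Visit 2".

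**The concern.** The baseline window carries the label of the screening period, but its visit list includes the visit at which treatment starts. A programmer who filters on visit number would put every Visit 2 record into baseline, including any taken during or after the infusion. An abnormality that first appears with the first infusion would then be read as a pre-existing condition of the patient.

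At stake is whether acute changes around the first dose can appear in the treatment-emergent tables at all. Section 6.13.5 also plans a listing of treatment-emergent abnormal vital signs and weight, which would inherit the same classification.

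**Working it through.** The SAP gives no figure to reproduce. The check sets the definitions side by side and follows a Visit 2 reading through them.

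**1. When dosing starts.** Section 5.1 puts the first infusion at Visit 2, Week 0, and Table 6.6.1 refers to treatment received at that visit. Visit 2 is therefore not purely a screening visit.

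**2. Which baseline rule governs.** The pre-dose default in Section 6.1 yields to a section that notes otherwise. For the categorical tables, Sections 6.13.5 and 6.13.6 do so: they name two visits and set no time limit within the second.

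**3. What follows for a Visit 2 reading.**

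| Timing of the reading | Literal rule | Baseline limited to pre-dose |
|---|---|---|
| Before the infusion starts | Baseline | Baseline |
| After the infusion starts | Baseline; cannot be treatment-emergent | Post-baseline; counts at any time |

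The two rules differ only in the second row.

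**4. Which criteria a baseline reading can meet.**

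- *Absolute ECG limits* (Appendix 2: heart rate, PR, QRS, QTcF). A single reading can meet them. Section 6.13.6 defines treatment-emergent high and low by parameter and direction, so an abnormal post-infusion Visit 2 value excludes the patient for that parameter in that direction.
- *Orthostatic blood pressure and pulse* (Appendix 1). These compare supine with standing and have no change-from-baseline part. A single assessment can meet them and exclude the patient for that parameter.
- *Sitting blood pressure, sitting pulse, weight and temperature* (Appendix 1), and *the QTcF change categories* (Appendix 2). All need a change from baseline. How a reading inside the baseline window could meet them is undefined, so exclusion does not clearly follow. The reading still cannot count as an event, because it is not post-baseline.

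**5. Direction of the effect, in symbols.** Take one arm and one parameter from the first two groups. Let N patients be normal on all pre-dose readings, let m of them be abnormal after the Visit 2 infusion, and let x of the other N − m be abnormal at a later visit.

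- Literal rule, any time: x / (N − m)
- Pre-dose baseline, any time: (x + m) / N
- Difference: (x + m)/N − x/(N − m) = m(N − m − x) / [N(N − m)]

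Since x cannot exceed N − m, the difference is never negative. The literal rule can understate the any-time proportion but cannot overstate it. It is zero when m = 0. The same m patients also leave the denominators of the semi-annual comparisons at Visits 8, 15, 22 and 28. The SAP gives no value for m or x.

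**The case against.** The strongest objection is that the effect depends on a schedule that the SAP does not show. No section says that vital signs or ECGs are taken after the Visit 2 infusion. If all are pre-dose, the visit-based window does no harm. The last-record rules do not show otherwise, because they cover repeats and rechecks at any visit. This stands, and it is why the point is conditional.

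A second objection is that the label of screening period shows a pre-dose intent: the aim is to use every pre-treatment assessment rather than only the last. The C-SSRS definitions in Section 6.13.9 describe the baseline measurement as the one just before treatment. That is probably what was meant, but the parenthesis names visits, and code written from it would follow the visits.

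A reader might also infer several stronger things that the SAP does not support:

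- *The patient drops out of the whole table.* Exclusion is by parameter and, for ECG, by direction.
- *Every later mean change is biased by a post-infusion baseline.* The visit-based definition sits only in the categorical paragraphs. Section 6.1 may still govern the continuous analyses, and the last-record sentence can be read consistently with a pre-dose baseline.
- *The rule conceals first-infusion effects from the DMC.* Section 6.16.1 gives the first interim analysis listings of vital signs, weight and ECGs that are not restricted to treatment-emergent values, and Section 6.16.2 carries them into the second.
- *A particular number of events is lost.* Any count needs assumed rates of post-infusion abnormality and of later abnormality, and the SAP supplies neither.

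**Conclusion.** The point holds as a defect in a stated rule. For the categorical vital-sign, weight and ECG tables, baseline is fixed by visit number, takes in the first-infusion visit and has no pre-dose limit. This conflicts with the separation of screening from treatment in Section 5.1 and departs from the default in Section 6.1.

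The consequence is conditional. If any vital sign or ECG, scheduled or unscheduled, is recorded after the start of the Visit 2 infusion, it is classed as baseline and cannot be treatment-emergent. For absolute ECG limits and orthostatic criteria, an abnormal value also removes the patient from that parameter's analysis (for ECG, in that direction). The error then runs towards under-counting. If no such reading exists, nothing changes. The size cannot be estimated from the SAP. This is a correction worth making because it is cheap and has no downside; it is not evidence that events have been lost.

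**What to change.** In Sections 6.13.5 and 6.13.6, replace the baseline sentence with wording to this effect:

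*For treatment-emergent abnormality analyses, baseline comprises all assessments at Visits 1 and 2 taken before the start of the first infusion. Where several records exist at a baseline visit, the last-record rule is applied only among these pre-dose records. Visit 2 assessments taken after the start of the first infusion are post-baseline and are included in the any-time analyses.*

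The cost is a small text change in each section and one comparison of assessment time with infusion start time in the programming. The SAP should also say how a Visit 2 record without a usable time is classified, since the comparison depends on it. If all Visit 2 readings prove to be pre-dose, the results do not change.
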